9.2. Missing Data

No imputation of missing data will be made. If any questionnaire (e.g., KSS) has a missing item, the total score for that scale will be considered missing.

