1.3. Clinical Data to Date

As of the interim analysis completed in December 2014, 220 patients were included across 5 centres between May 2009 and December 2013. The mean age, height and weight were 65.3 years, 171.4 cm and 87.9 kg, respectively. All patients received a Scorpio NRG Total Knee System.

The mean assessment and functional components of the Knee Society Score were 57.6 and 61.7 pre-operatively compared to 83.6 and 88.7 at the 1-year follow-up, respectively. Patient scores including the LEAS, KOOS, SF-36 and EQ5D showed an increase between the pre-operative visit and 1-year follow-up visit. There were three prosthesis revisions reported during the first year of follow-up and three patients have decided to withdraw from the trial. This analysis was carried out in the early stages of follow-up, so it is not possible to draw any conclusions about the performance of the prosthesis in this report.

Overall, the patient group showed improved clinical results in early follow-up.

2. Objectives of the Clinical Investigation

The objective of this study is to collect basic function and patient satisfaction data for observation and analysis.

Specific objectives include the following:

- Evaluate the effect of component design on functional performance by comparing postoperative Knee Society Scores with preoperative.
- Evaluate the effect of component design on patient activity by comparing postoperative Lower Lower Extremity Activity Scale (LEAS) with preoperative.
- Evaluate patient satisfaction using SF-36[®] Health Survey.
- Evaluate quality of life using Knee Injury and Osteoarthritis Outcome Score (KOOS) and EuroQol 5D (EQ-5D).

3. Design of the Clinical Investigation

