5.5. Supplies/Device Accountability

The study devices must be stored and handled in accordance with the manufacturer's guidelines. The Investigator will also keep accurate records of the devices assigned to each subject.

The investigator will be asked to attach the labels (with the lot device number), where possible, of the implanted devices to the corresponding patient CRF page in order to keep a tracking of the devices.

6. Evaluations

Subjects will be evaluated preoperatively and at follow-up intervals of three months, one year, three years, five years and an optional seven years (see Tables 1 and 2). Each subject will be followed for a minimum of five years post-implantation. All subject evaluations will be documented by completion of appropriate Case Report Forms.

Table 2 – Evaluation schedule (functional and patient assessment)

Evaluation	Pre-OP	Intra-OP	Prior to discharge	3 months (± 3 weeks)	1 year (± 2 months)	3 years (± 2 months)	5 years (± 3 months)	7 years** (± 3 months)
Demographics	x							
Medical history	x							
Clinical evaluation	x		x	x	x	x	x	x
Surgical details		x						
KSS	x			x	x	x	x	x
Lower Extremity Activity Scale	x			x	x	x	x	x
KOOS	x				x		x	x
SF-36	x			x	x	x	x	x
EQ-5D	x			x	x	x	x	x
*Radiographs: ap, lateral	x		x		x		x**	x
*Radiograph: merchant view	x			x				
*Radiograph: long leg	x			x				

*Radiographs will not go into analysis

**optional

Basic demographic and medical history information are to be collected at the most two months prior to surgery. This information includes age and gender. Height, weight, primary diagnosis, concurrent medical condition and prior treatment to the affected joint are also documented at this time.

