6.2. Functional Evaluation

All subjects participating in the study are to be evaluated functionally utilizing the KSS, LEAS, KOOS, and EQ-5D preoperatively and at each protocol specified follow-up interval (see Table 2). Clinical assessment is based on an evaluation of pain and function.

Specific parameters include:

- Pain intensity
- Range of motion
- Stability
- Anatomic alignment
- Walking/standing ability
- Stair climbing ability
- Use of walking aids

To allow for accurate measurement of the range of motion a goniometer should be used. It is of particular importance that a sterile goniometer is used during the surgery to measure the intraoperative range of motion.

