6.3. Patient Assessment Evaluations

Data will be obtained from the subjects with the use of standard health status questionnaires. The SF-36 is designed to measure overall evaluation of health, functional status and wellbeing from the subject's perspective. The LEAS is designed to measure patient activity. The patient's quality of life will be measured by the KOOS and EQ-5D. Subjects will be asked to complete the questionnaires preoperatively and at each follow-up evaluation interval specified in the protocol (see Table 2).

7. Adverse Events

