10.1. Study Monitoring Plan

This investigation will be monitored regularly by monitors appointed by Stryker to review the compliance with the clinical investigation plan, ISO 14155 and with applicable regulatory requirements. Proper monitoring ensures adequate protection of the rights of human subjects, the safety of subjects involved in a clinical investigation and the quality and integrity of data submitted as a result of the investigation.

This study will be monitored depending on the recruitment rate. The first monitoring visit is to take place after the recruitment of the first patient and then at least quarterly during the enrolment period and at least twice per year during the follow up periods, with additional visits as necessary. The investigator will allocate adequate time for such monitoring activities. The Investigator will also ensure that the monitor or other compliance or quality assurance reviewer is given access to all study-related documents and study related facilities and has adequate space to conduct the monitoring visit.

The monitor will review the source documents and compare them to the data contained in the case report forms, in addition to performing a periodic review of the Investigator Site File. The monitors will need the following when they visit:

- An area where they can review records
- Patient case report forms
- Signed Patient Informed Consents
- Source documents (Patient charts, radio graphs, etc.)
- Investigator Site File
- Time to meet with the study coordinator and the Investigator

Clinical data reports are considered as containing source data and are therefore regarded as confidential and available for review only by the sponsor's authorised representative, clinical investigators and their ethics committees or by regulatory authorities if required for audits.

The sponsor's clinical monitor will check data accuracy and quality before taking the case report forms and leaving a copy on side. Informed consent and source data relevant to the study are inspected but are not be removed from the side.

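### Section 9.2 voids a scale's total for one blank item and names no sensitivity analysis, so nearly complete patient questionnaires such as KOOS and SF-36 can be lost from the non-primary score objectives

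*Combined protocol and SAP*

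**What the plan says.** Section 9.2 is two sentences long. The first is "No imputation of missing data will be made". The second is "If any questionnaire (e.g., KSS) has a missing item, the total score for that scale will be considered missing". The KSS appears only as an example, so the rule reaches every questionnaire in the study. Sections 9.1, 9.2, 10.2 and 10.3 contain no minimum number of answered items, no partial-scoring rule and no sensitivity analysis.

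The scores carry all the specific objectives in section 2, for instance "Evaluate quality of life using Knee Injury and Osteoarthritis Outcome Score (KOOS) and EuroQol 5D (EQ-5D"). On how they are collected, section 6.3 says: "Data will be obtained from the subjects with the use of standard health status questionnaires". Table 2 schedules SF-36 preoperatively and at 3 months, 1, 3 and 5 years. It schedules KOOS preoperatively and at 1 and 5 years only. A 7-year visit is optional for both. The primary endpoint in the Study Summary is survival (revision rate), which is not a questionnaire score.

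**The concern.** A patient who answers every item but one loses that score, although the remaining answers are in the database. The patients who contribute to a score can then differ from visit to visit for a reason the scoring rule creates.

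KOOS has the least slack, with only two required postoperative assessments per patient. One blank can void one of those two, or the single preoperative score from which change is measured. Section 1.1 describes a postoperative-to-preoperative comparison for KOOS, and the interim report makes one: "Patient scores including the LEAS, KOOS, SF-36 and EQ5D showed an increase between the pre-operative visit and 1-year follow-up visit".

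Two wording gaps add to this. Section 9.2 does not say whether a scale is a subscale or the whole questionnaire. It also does not say whether an item entered as N/A under 10.2 counts as missing. Two analysts could follow 9.2 and produce different datasets. The loss could also go unnoticed: the summaries that 9.1 lists for continuous variables do not include the number of non-missing values, and no count of voided scores is required.

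**Working it through.** **No figure to reproduce.** The documents give no item-level missing rate, subscale length or clustering of blanks, and the 250 patients in section 3.3 come without a power or precision basis. What follows is an illustration on assumed inputs.

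**Inputs**
- Rule: one blank voids the score (9.2).
- p, the chance that an item is blank: assumed 0.1%, 1% or 2%.
- m, the number of items: 10 for an assumed subscale; 36 for SF-36 voided as one unit (item count taken from its name in the abbreviations list).
- r, the correlation of blanks within a form: assumed 0 (independent), 0.1 or 0.3.

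**Formulas**
- Loss per visit = 1 − P(no blank).
- Independent blanks: P(no blank) = (1 − p)^m.
- Clustered blanks (beta-binomial): P(no blank) = product over i = 0 to m − 1 of (b + i)/(a + b + i), with a = p(1 − r)/r and b = (1 − p)(1 − r)/r.

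**Worked case, m = 10 and p = 1%**
- r = 0: 1 − 0.99^10 = 9.6%.
- r = 0.1: a = 0.01 × 0.9/0.1 = 0.09 and b = 0.99 × 0.9/0.1 = 8.91. The product of (8.91 + i)/(9 + i) for i = 0 to 9 is 0.932, so the loss is 6.8%.

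**Scores voided per visit**

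| Items | p | r = 0 | r = 0.1 | r = 0.3 |
|---|---|---|---|---|
| 10 | 0.1% | 1.0% | 0.7% | 0.4% |
| 10 | 1% | 9.6% | 6.8% | 4.2% |
| 10 | 2% | 18.3% | 13.1% | 8.3% |
| 36 | 0.1% | 3.5% | 1.5% | 0.7% |
| 36 | 1% | 30.4% | 13.9% | 6.8% |
| 36 | 2% | 51.7% | 25.9% | 13.2% |

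If all 250 planned patients returned a form, the 10-item range would be about 1 patient (250 × 0.00432 = 1.1) to about 46 (250 × 0.18293 = 45.7) per visit.

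**How many voided scores are nearly complete?** The share with exactly one blank is P(one blank)/P(at least one blank). For 10 items it runs from 45.5% (p = 2%, r = 0.3) to 99.6% (p = 0.1%, r = 0). For 36 items with r of 0.1 to 0.3 it is lower, about 30% to 49%.

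All these figures are before any recovery through the checks in 10.1 to 10.3.

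**The case against.** **The rule is clear and assumption-free.** It is set in advance, contradicts nothing else in the plan and assumes nothing about unanswered items. For the KSS, its only named example, it is defensible. Section 6.2 says "Clinical assessment is based on an evaluation of pain and function" and lists pain, range of motion, stability, alignment and so on. If those are the KSS components, they are unlike items that should not stand in for one another. This stands, and the KSS is left out of the point. The documents do not show that LEAS or EQ-5D are summed from several items, so nothing is claimed for them either.

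**Prevention is already planned.** Under 10.2 forms are completed promptly, the investigator answers for completeness and gaps must be explained. Under 10.1 the monitor compares forms with source, and under 10.3 omissions trigger a clarification form. These steps will recover some items, especially those the clinician recorded. They do not change the scoring rule. Monitoring in follow-up is promised only "at least twice per year during the follow up periods, with additional visits as necessary", and Data Management raises queries on receipt of the forms, so a patient's blank may surface months after the visit it describes.

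**Size is not shown.** Correct. The 10-item range is wide and its low end is negligible. A reader might infer that half the SF-36 data are at risk. That needs SF-36 voided as one unit, 2% blanks and full independence together; with r = 0.3 the same case gives 13.2%.

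**Other readings that go too far.** A reader might infer that the study's main result is weakened, or that the scores are biased. The primary endpoint does not use questionnaires. Bias would need blanks to depend on the patient's condition, which the documents do not show. A reader might also infer that 9.2 breaks the instruments' own scoring rules; the documents neither state nor cite such rules.

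**Timing.** Scores were reported at the December 2014 interim analysis. Changing the main scoring rule afterwards is a real cost, and the fix has to allow for it.

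**Conclusion.** The point holds as a cheap improvement, with medium confidence. Following 9.2 discards answers already collected on nearly complete patient questionnaires, such as KOOS and SF-36, and the plan offers no analysis that would show the effect. The scores affected serve the specific objectives in section 2; calling them non-primary is an inference from the stated primary endpoint.

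The actual loss is unknown and may be small. The 0.4% to 18.3% per visit rests on three assumptions: a 10-item subscale, item gaps of 0.1% to 2%, and within-form correlation of 0 to 0.3. The larger 36-item figures apply only if 9.2 is read as voiding the whole SF-36.

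**What to change.** Keep the first sentence of 9.2, so that non-questionnaire variables such as range of motion, and wholly missing forms or visits, remain without imputation. Add to it: *except as stated below for single items of patient-completed questionnaires*. Replace only the second sentence with:

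> Multi-item patient-completed questionnaires are scored at subscale level using the instrument's published missing-item rule where one exists; the KSS and any instrument without such a rule are scored only when all items are complete. Items marked N/A are treated as unanswered for scoring and counted separately. The number of voided and partly scored scales is reported at each visit, and all scores are also reported under the strict any-item-missing rule.

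The sponsor should cite the rule used for each instrument. The text works either way, because an instrument without a published rule stays under complete-item scoring.

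The cost is wording and a scoring program; no new data are needed. There are two downsides: a mild assumption within subscales for partly answered forms, and a scoring change made after interim scores were seen. Reporting both sets of results side by side makes the effect of the change visible. If the sponsor prefers, the strict rule can stay as the main analysis with partial scoring as the sensitivity analysis. Even then, 9.2 should define the scale, settle N/A items and require the counts.

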9.3. Protocol Deviations

Any deviation from this protocol will be recorded with an explanation for the deviation and reported to Stryker who is responsible for analysing them and assessing their significance. Protocol deviations will be reported to the IEC/IRB according to the local IEC/IRB's reporting procedures.

Protocol Deviations for this study include the following:

- Informed consent process is not carried out according to ISO 14155
- Subject enrolled does not meet the inclusion/exclusion criteria.
- Subject is not implanted with study device.
- Subject not seen in the specified follow-up window.
- Surgical protocol not followed.

If the site anticipates a possible protocol deviation, the investigator or study coordinator should contact Stryker for guidance. For the examples cited above, it is likely that the patient would be excluded, and a Study Termination form completed.

10. Quality Management

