Title	Scorpio NRG[®] prospective, open-label, post-market international multicentre outcome Study
Protocol Number	K-S-002 (previous protocol number SLCRG-001-2007)
Phase	Post-marketing
Sponsor	Stryker Orthopaedics Mahwah, USA
Study design	Prospective, open-label, international
Study Duration	12 months enrolment period + up to a minimum of 5 years follow-up for each case = ~ 6 years total duration.
Study Centre(s)	5
Objectives	To collect basic function and patient satisfaction data for observation and analysis. Specific objectives include the following: Evaluate the effect of component design on functional performance by comparing postoperative Knee Society Scores with preoperative. Evaluate the effect of component design on patient activity by comparing postoperative Lower Extremity Activity Scale (LEAS) with preoperative. Evaluate patient satisfaction using SF-36 [®] Health Survey. Evaluate quality of life using Knee Injury and Osteoarthritis Outcome Score (KOOS) and EuroQol 5D (EQ-5D).
Primary endpoint	Survival (revision rate)
Indication	Primary total knee replacement
Study device / control device	Scorpio NRG [®] Total Knee System
Number of Subjects	250 Patients (Competitive recruitment)

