4.3. Discontinuation and Withdrawal of Subjects

The subject's participation in this investigation is voluntary, and the subject has the right to refuse further participation or withdraw from this investigation at any time and without providing a reason.

In the event that a subject is discontinued from the study for any reason, the site will complete a Study Termination form. Subjects may be withdrawn for the following reasons:

- Serious Adverse Event
- Patient Withdrawal
- Revision/Removal of study device
- Lost to Follow-Up
- If, in the Investigator's opinion, continuation in the study would be detrimental to the subject's wellbeing.
- At the specific request of the Sponsor
- Completion of study and final evaluation

If the patient fails to return for their follow-up appointments, every effort should be made to contact the subject to assess their health status. If after attempting to contact the patient

through three documented phone calls. If the patient still does not respond, the patient will be considered as “lost to follow-up”. A Study Termination Form will be completed after notifying Stryker of the patient’s status.

In the event that the subject is discontinued by the investigative site prior to the final study evaluation, the subject is notified that they are no longer in the study and a Study Termination form will be completed.

Following discontinuation, the subject will be seen regularly as considered clinically appropriate. If the discontinuation was caused by an adverse event the subject will be seen regularly until the symptoms have disappeared or are under control, or until feasible treatment has been undertaken. Refusal to participate or early withdrawal from this investigation will not affect the quality or availability of the subject’s medical care.

Subjects withdrawn from the study will keep their subject number. New subjects must always be assigned a new subject number. In the event that the subject withdraws from this investigation, the information that has already been collected will be included in the database and in the final analyses. The subject’s medical records will also be available for monitoring, auditing and inspection purposes.

5. Subject Enrolment

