9.1. Statistical Methods

Descriptive statistics will be computed for all baseline conditions and demographic parameters. For parameters represented by continuous variables (e.g., ROM), the summaries will consist of the mean, median, standard deviation, minimum, and maximum values. For categorical variables, the number and percent in each category will be presented. If appropriate, the data will be presented by appropriate subgroups (e.g., centre, gender). Descriptive statistics and statistical comparisons for important demographic, efficacy, and safety variables will be provided in tables.

A survival analysis will be performed to according to the number of revision surgeries.

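### Section 9.3 makes exclusion and termination likely after an out-of-window visit or a surgical deviation, in conflict with sections 4.3, 6, 6.1 and 8.3, while section 9.1 gives the primary revision analysis no analysis set or censoring rule

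*Combined protocol and SAP*

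**What the plan says.** Section 9.3 lists five deviations: a faulty consent process, failure to meet eligibility, no study device implanted, "Subject not seen in the specified follow-up window" and "Surgical protocol not followed". The sponsor judges their significance, with no criteria given, and a site that foresees a deviation is to ask the sponsor for guidance. The section closes: "For the examples cited above, it is likely that the patient would be excluded, and a Study Termination form completed".

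Other sections bear on the same events:

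- Section 4.3, missed visits: the site tries to reach the patient. Only after three documented calls without response is the patient classed as lost and a termination form completed.
- Section 4.3, discontinuation: "In the event that a subject is discontinued from the study for any reason, the site will complete a Study Termination form". The listed reasons do not include protocol deviation but do include "At the specific request of the Sponsor". A discontinued patient is told that they have left the study. Data already collected from a patient who withdraws stay in the final analyses.
- Section 6: "Each subject will be followed for a minimum of five years post-implantation".
- Section 6.1: departures from the site's surgical procedure are documented. No termination is mentioned.
- Section 8.3: a deviation made to protect the patient is reported to the ethics committee on a deviation form. Again no termination is mentioned.
- Section 7.4: adverse event collection runs to the last visit or last contact.

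The study summary gives survival, as revision rate, as the primary endpoint. Its whole analysis in section 9.1 is: "A survival analysis will be performed to according to the number of revision surgeries".

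**The concern.** Visit-window and surgical deviations arise in patients who already carry the implant and are at risk of the primary event. A rule that makes their termination likely ends observation of that event for a reason that may be linked to it: a patient with a failing knee may attend late, and a difficult operation may both depart from the procedure and carry more risk. The threshold is left open (one visit or several, any surgical departure or only a serious one), and so is the meaning of exclusion.

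Section 9.1 does not settle the matter, because it does not say who is analysed or when observation stops. Two analysts could follow the plan faithfully and produce different revision estimates. In a single-arm, open-label study the sponsor would be deciding, case by case and possibly with the outcome known, who stays under observation.

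**Working it through.** **Text.** The conflict needs no arithmetic. For a missed visit, 4.3 requires contact attempts and then loss to follow-up, while 9.3 points to exclusion. For a surgical departure, 6.1 and 8.3 require documentation or a report, while 9.3 points to exclusion. Section 6 sets a five-year minimum for every patient. The plan gives no precision figure to reproduce: 250 patients are stated without a target rate or error level.

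**Size, illustration only.** From the documents: 220 patients (section 1.3) and visits at 3 months, 1, 3 and 5 years (Table 2). Assumed: 4% revised by five years, so 220 × 0.04 = 8.8 revisions; constant hazard −ln(0.96)/5 per year; chance p of 5, 10 or 15% that a visit is out of window, independent across visits.

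- All patients kept: SE = √(0.04 × 0.96/220) = 1.3 points.
- One-miss rule, terminated before the five-year visit: 220 × [1 − (1 − p)³] = 31, 60, 85.
- One-miss rule, including a first miss at the five-year visit: 220 × [1 − (1 − p)⁴] = 41, 76, 105. The extra patients lose no follow-up relevant to a five-year estimate if they are censored.
- Two-miss rule, terminated before the five-year visit: 220 × [3p²(1 − p) + p³] = 1.6, 6, 13.
- Revisions unobserved, one-miss rule: the shares of five-year revisions falling in 0–0.25, 0.25–1, 1–3 and 3–5 years are 0.051, 0.152, 0.402 and 0.395. Each share is multiplied by 1 − (1 − p)^k, with k = 0, 1, 2, 3 earlier visits. The sum u is 0.103, 0.199, 0.287, and 8.8u is 0.91, 1.75, 2.52.
- Deletion instead of censoring, unrelated misses, one-miss rule: 0.04(1 − u)/[0.04(1 − u) + 0.96(1 − p)⁴] = 4.4, 4.8, 5.4%. The estimate rises because patients revised early have fewer visits to miss.

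Kaplan–Meier estimates in the table are from simulation (6,000 replicates, n = 220). “Doubled” and “tripled” refer to the miss chance at the last visit before a revision.

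| Five-year estimate (true value 4%) | p = 5% | p = 10% | p = 15% |
|---|---|---|---|
| One miss, censored, unrelated (SE, points) | 4.0% (1.4) | 4.0% (1.5) | 4.0% (1.6) |
| One miss, censored, doubled | 3.8% | 3.6% | 3.4% |
| One miss, censored, tripled | 3.6% | 3.2% | 2.7% |
| One miss, deleted, unrelated | 4.4% | 4.8% | 5.4% |
| One miss, deleted, tripled | 4.0% | 3.9% | 3.7% |
| Two misses, censored, unrelated | 4.0% | 4.0% | 4.0% |
| Two misses, censored, tripled | 4.0% | 3.9% | 3.8% |

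**Surgical deviations.** Suppose a share f of patients is removed at surgery and their risk is k times that of the rest. The estimate is then 4/(1 − f + fk)%. For f = 5, 10, 20% this gives 4.0% throughout at k = 1 and 3.8, 3.6, 3.3% at k = 2. These shares and risk ratios are also assumptions.

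**The case against.** Several objections have force.

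- **Discretion and context.** The sentence says only that exclusion is likely, and it follows advice about deviations that a site anticipates. It can be read as guidance on cases raised beforehand. That softens it, but a late visit and a surgical departure are among the examples it covers, and no criteria guide the decision.
- **Data kept.** A reader might infer that 9.3 deletes patients from the analysis. The documents do not establish this. The termination form serves every discontinuation, sponsor request is a listed reason, and 4.3 keeps the data of patients who withdraw. Discontinuation with censoring is the more natural reading. It is not certain, because the data sentence speaks only of withdrawal.
- **Later revisions.** A reader might infer that a revision after termination cannot be recorded. That is too firm: 7.4 extends to last contact, and 4.3 has discontinued patients seen as clinically appropriate. But that is clinical care, and no route for collecting the endpoint is described, so probable loss is the fair statement.
- **Five-year minimum.** Any discontinuation rule sits awkwardly with section 6. This conflict is weaker than those with 4.3, 6.1 and 8.3.
- **Assumption-driven size.** This stands. No miss rate, deviation rate or five-year revision rate is given, and the larger shifts need the strictest rule together with misses related to revision.

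**Conclusion.** The point holds as a contradiction between sections and a gap in the primary analysis, and it should be fixed. On the more natural reading (data kept, patient censored), the cost is lost precision, with bias only if the deviation is related to revision risk. If exclusion means deletion, the estimate can move either way.

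The size is not derivable from the documents. Under the stated assumptions, a one-miss rule matters and a two-miss rule hardly does, so the unstated threshold decides.

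Two stronger conclusions are not supported. One is that the reported revision rate is biased, or biased downward: with data kept and unrelated misses there is no bias. The other is that patients have been removed in this way: section 1.3 reports three first-year revisions and three patients who chose to withdraw, and no termination for a deviation. That does not rule such terminations out, which is why a count is needed.

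Timing limits the remedy. This version is dated January 2019. If the last patient was included in December 2013 (section 1.3 gives that month for the interim cohort but does not confirm the end of enrolment), the last five-year window closed about March 2019, so the follow-up part mainly affects the optional seven-year visit. The analysis set, censoring rule and termination count concern the whole cohort.

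**What to change.** 1. In 9.3, limit the last sentence to subjects without valid consent or not implanted with the study device, so that these two cases keep a stated consequence. Add: *Visit-window, surgical-protocol and eligibility deviations in implanted, validly consented subjects are recorded and reported, but do not by themselves end study follow-up or remove the subject from analysis.* Reconcile this with 4.3, 6.1 and 8.3.
2. In 9.1, add: *The survival analysis includes all validly consented subjects implanted with the study device, from surgery to revision, using actual dates, censored at death, withdrawal, loss to follow-up or last contact. Subjects already terminated for a deviation stay in the set and are censored at last contact.*
3. Report the number, timing and deviation type of any terminations made under 9.3. Show a deviation-free analysis only as a sensitivity analysis.

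The cost is a narrowed sentence and an added one in 9.3, a short paragraph in 9.1, one count and one sensitivity table. The downside is slightly wider visit timing in the score summaries.
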